9.1.3 Unanticipated Adverse Device Effects

An **unanticipated adverse device effect (UADE)** means any serious adverse effect on health or safety or any life-threatening problem or death caused by or associated with a device, if that effect, problem, or death was not previously identified in nature, severity, or degree of incidence in the investigational plan or application, or any other unanticipated serious problem associated with a device that relates to the rights, safety, or welfare of subjects.

An event will not be considered a UADE if it is a known consequence of the underlying disease or condition under investigation, surgery, or other events that commonly occur in the study population independent of the investigational device.

The final determination of whether an AE meets the definition of a UADE will be made by the independent adjudication committee for this study.

9.2 Adverse Event Recording and Reporting

9.2.1 Adverse Event Recording

Investigators are responsible for providing a description of all AEs, including the clinical outcome for the subject. Investigators will evaluate each event for seriousness, severity, and relatedness to the procedure, device, or stimulation therapy. Investigators must supply the Sponsor with any additional information related to safety reporting of a particular event.

9.2.2 Adverse Event Reporting

Investigators are required to report all AEs from the time of consent (except as outlined below). If an AE leads to multiple outcomes that sequentially worsen, only the worst AE will be reported.

Investigators shall report AEs to the Sponsor, and to their reviewing IRB per the IRB's reporting requirements. Investigators are required to report UADEs to the Sponsor and their reviewing IRB as soon as possible, but in no event later than 10 working days after the Investigator first learns of the effect, per 21 CFR 812.150 (refer to section 13.7.2 for Investigator reporting requirements).

AE reporting exceptions:

- AEs that would be reasonably expected to be associated with any surgical procedure (e.g., anesthesia associated symptoms, surgical site pain, post-procedure pain) will not be required to be reported as AEs unless, in the opinion of the Investigator, the nature and/or severity is outside of what is typical for SCS procedures and recovery.
- Lack of efficacy, by itself, does not constitute an AE since failure to receive therapeutic benefit is an issue of efficacy, not safety.
- Loss of therapy/stimulation does not constitute an AE unless an untoward medical occurrence results.
- A subject's perception of the stimulation induced feeling of stimulation sensation is called paresthesia. There are well-known challenges associated with optimizing SCS such as changes in stimulation intensity and stimulation in unwanted areas. These will not be reported as AEs unless the Investigator determines the nature and/or severity is outside what is typical for neurostimulation.
- Temporary changes in symptoms and stimulation that are alleviated with programming will not be reported as AEs unless the Investigator determines the nature and/or severity is outside what is typical for neurostimulation.

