9.3 Independent Medical Reviewer and/or Adjudication Committee

Independent medical reviewer and/or adjudication committee will be responsible for the review, evaluation, categorization, and adjudication of all AEs that occur during the clinical study. AEs will be reported based on this adjudication.

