11.3 General Statistical Procedures

The following general statistical methods will be employed to assess the study data:

- There are no pre-planned formal statistical hypothesis tests.
- Standard summary statistics will be used to summarize key study variables. Categorical variables will be summarized via incidence and percent. Continuous variables will be summarized via mean, median, standard deviation, and range.
- Findings of significance may be presented and include p-values and/or 95% confidence intervals as appropriate.
- Standard tests for significance will be employed, including one sample t-tests. Additional exploratory analyses may be performed and include correlation analysis, linear and logistic regression analyses, repeated measures analyses, and generalized estimating equation (GEE) analyses as appropriate.
- Unless stated otherwise, statistical significance is defined as achieving a p-value less than 0.05. P-values will be nominal and not adjusted for multiplicity.
- In the event planned parametric methods are found to be inappropriate based upon observed distributions of individual variables, appropriate non-parametric methods will be employed.
- The incidence of all distinct AEs will be presented. AEs will also be summarized by seriousness, severity, and relatedness to the procedure, device, and/or stimulation. AEs will be reported based on the adjudication committee determination.

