12 RISK ANALYSIS

12.1 Potential Risks

Risks associated with the Evoke System are similar to those of other open-loop SCS systems, which are generally minor. All medical procedures involve some risk of injury, including death. Other anticipated risks associated with the Evoke System are listed in this protocol or found in the literature, post-market surveillance data (e.g., FDA Manufacturer and User Facility Device Experience (MAUDE) database), and device labeling for SCS systems. Please refer to the current Evoke IFUs for the most up-to-date risks associated with the Evoke System.

In addition to the general surgical risks, potential risks to subjects associated with implantation and use of the Evoke System include, but are not limited to:

- Undesirable changes in stimulation sensation and/or location
- Uncomfortable changes in stimulation (over and/or under stimulation)
- Persistent post-surgical pain at hardware implantation sites
- CLS migration, which may result in pain or difficulty in charging
- Seroma or hematoma at surgery sites
- Epidural hemorrhage, spinal cord injury and possible paralysis
- Lead migration from the location chosen at initial implantation resulting in stimulation changes
- Breakage of the lead or failure of other system components, which may result in loss of stimulation
- Rejection of, or allergic reaction to, the implanted components
- Infection that may require hospitalization with intravenous antibiotic therapy
- Cerebrospinal fluid (CSF) leakage
- Inadequate pain relief following system implantation
- Erosion of the lead or CLS through the skin
- Weakness, clumsiness, numbness or pain

Subjects may require surgery (including revision, explant, and replacement) as a result of any of the above.

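### The worst-only AE reporting rule in Section 9.2.2 is not limited to one diagnosis, so precursor AEs that Section 11.3 means to count can go unreported

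*Combined protocol and SAP*

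**What the plan says.** Section 9.2.2 begins with a broad duty: "Investigators are required to report all AEs from the time of consent (except as outlined below"). The next sentence narrows it: "If an AE leads to multiple outcomes that sequentially worsen, only the worst AE will be reported". This sentence stands apart from the bulleted list of reporting exceptions further down the section.

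Three other sections are written as if every event reaches the dataset:

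- Section 9.2.1: "Investigators are responsible for providing a description of all AEs, including the clinical outcome for the subject", and "Investigators will evaluate each event for seriousness, severity, and relatedness to the procedure, device, or stimulation therapy".
- Section 9.3: the independent reviewer or committee is responsible for "review, evaluation, categorization, and adjudication of all AEs that occur during the clinical study".
- Section 11.3: "The incidence of all distinct AEs will be presented", with further summaries by seriousness, severity and relatedness, all based on adjudication.

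The term *distinct* is not defined. Section 12.1 lists seroma or hematoma, CSF leakage, lead migration and infection as separate potential risks.

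**The concern.** The worst-only rule acts at the site, before adjudication and analysis. If it applies to a chain of different diagnoses, the site reports the last and worst event and may leave out the one that started the chain. Adjudicators cannot classify an AE they do not receive, and the Section 11.3 tables cannot count it.

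Continued safety evidence is one of the study's stated aims (Section 2.5). There are no pre-planned hypothesis tests, and the sample size rests on the precision of an event incidence, so descriptive incidence is a main product of the study. An under-reported precursor lowers the incidence of its event type. If precursor and sequel would have been judged differently for relatedness, the split between procedure, device and stimulation shifts too. With up to 25 sites, an unclear rule may also be applied differently from site to site.

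**Working it through.** **Step 1: what the sentence selects among.** The sentence is causal (one AE leads to several outcomes), and what it tells the site to keep is the worst *AE*. The members of the chain are therefore treated as AEs in their own right. A rule about grading one diagnosis would normally speak of the worst severity. No other text confines the sentence to one diagnosis or says that superseded AEs are retained for counting.

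**Step 2: one chain followed through the sections.** Take a seroma that leads to an infection.

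| Section | Seroma | Infection |
|---|---|---|
| 12.1, listed as its own risk | yes | yes |
| 9.2.1, described and evaluated | expected | expected |
| 9.2.2, reported under the worst-only rule read literally | no | yes |
| 9.3, adjudicated | expected, but only possible if received | yes |
| 11.3, counted as a distinct AE | expected, but only possible if received | yes |

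For this chain, 9.2.2 read literally cannot be followed together with the other three. One quantity is not affected: the proportion of subjects with at least one AE, because one event from each chain is still reported. The incidence by event type and the summaries by relatedness are affected.

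**Step 3: the plan's own figure.** Section 11.1 states a precision of about ±6% or smaller for 300 subjects at 50% incidence, with an exact two-sided 95% interval. With x = 150 and n = 300, the Clopper-Pearson limits are the 0.025 quantile of Beta(x, n − x + 1) and the 0.975 quantile of Beta(x + 1, n − x): 44.20% and 55.80%, a half-width of 5.80 points. The figure is reproduced and is not in dispute. It describes sampling error only and takes no account of events that were never reported.

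**Step 4: size, by assumption only.** Let p be the true incidence of a precursor event and f the share of these events absorbed into a worse AE. Reported incidence = p × (1 − f), so the proportional loss is f. The documents give neither p nor f; all values below are assumed. Counts are out of 300 and rounded to whole subjects (halves to the even number).

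| p (subjects) | f | Reported | Incidence | Exact 95% interval |
|---|---|---|---|---|
| 3% (9) | 10% | 8 | 2.67% | 1.16 to 5.19% |
| 3% (9) | 25% | 7 | 2.33% | 0.94 to 4.75% |
| 3% (9) | 50% | 4 | 1.33% | 0.36 to 3.38% |
| 5% (15) | 10% | 14 | 4.67% | 2.57 to 7.71% |
| 5% (15) | 25% | 11 | 3.67% | 1.84 to 6.47% |
| 5% (15) | 50% | 8 | 2.67% | 1.16 to 5.19% |
| 10% (30) | 10% | 27 | 9.00% | 6.01 to 12.82% |
| 10% (30) | 25% | 22 | 7.33% | 4.65 to 10.89% |
| 10% (30) | 50% | 15 | 5.00% | 2.83 to 8.11% |

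In eight of the nine rows the interval still contains the assumed true incidence; in the last it does not. Enrollment is defined at the trial procedure and not every subject need be implanted, so denominators for implant events may be below 300. The proportional loss f does not depend on the denominator.

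**The case against.** The sentence has a narrower reading: a single AE that progresses and is reported once, at its worst. On that reading nothing conflicts with counting distinct AEs. Section 9.2.1 can also be taken as a recording duty and 9.2.2 as a reporting duty, with the description of the worst AE carrying its history. And because *distinct* is undefined, a contradiction with 11.3 cannot be shown on every reading. All of this is fair. But the text does not choose the narrower reading, and its reference to the worst AE points the other way. A history inside another event's narrative also does not yield an incidence for the precursor.

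A reader might infer that a lead migration followed by revision, infection and explant would leave no trace of the migration. The documents do not support that. Section 8.8 collects procedure data, adverse events and device deficiencies at every revision, replacement and explant. Section 10.2 requires suspected device deficiencies to be reported, and any associated AE with them. The chain is also a poor fit to the rule: revision and explant are interventions, and an infection after revision surgery is not plainly a worse form of migration. More generally, safety is evaluated at every visit in Table 4, so a precursor may be reported before its sequel occurs, and 9.2.2 does not tell sites to withdraw it. These routes rule out total loss. They do not cover every precursor (a seroma is not obviously a device deficiency), and they do not guarantee that a precursor enters the 11.3 incidence.

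It is also tempting to add that onset dates move to the later event, or that the lost events are mostly device-related. The documents contain no onset-date rule and do not classify precursors by relatedness, so neither claim can be made. The CRF is not among the documents, so it may already link events.

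**Conclusion.** The point holds as a reporting rule that is too broad as worded and conflicts with 9.2.1, 9.3 and 11.3 when followed literally. Under that reading, the incidence of precursor events is biased downward and the relatedness split may shift. The downward direction depends on the literal reading; if every site applied the rule only within one diagnosis, there would be no bias.

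The size cannot be established from the documents. It equals the share of precursor events absorbed into a worse AE, which may be small if such chains are rare. No pre-planned hypothesis test depends on it. The correction is still worthwhile, because safety incidence is a main output and events not reported at the time may be hard to recover later.

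**What to change.** Replace the worst-only sentence in 9.2.2 with a rule along these lines:

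- Where the same diagnosis worsens, report it once, at its worst severity.
- Where one AE leads to a different diagnosis, report each as its own AE, with its own seriousness, severity and relatedness.
- Record the link between an AE and its precursor, and show linked chains in the AE listing, so that one episode is not read as several independent ones.

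Define a distinct AE in the same terms in 11.3, so that 9.2.1, 9.2.2, 9.3 and 11.3 agree.

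The cost is a short protocol change and, if the AE form does not already have one, a field for the linked event. Sites complete slightly more AE forms and the total AE count rises, which the links explain. Only reporting changes; clinical management is not affected.

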9.3 Independent Medical Reviewer and/or Adjudication Committee

Independent medical reviewer and/or adjudication committee will be responsible for the review, evaluation, categorization, and adjudication of all AEs that occur during the clinical study. AEs will be reported based on this adjudication.

10 DEVICE DEFICIENCIES

10.1 Device Deficiency Definitions

A device deficiency is an inadequacy of a medical device with respect to its identity, quality, durability, reliability, safety or performance. Device deficiencies include malfunctions, use errors, and inadequate labelling.

10.2 Device Deficiency Reporting

The Investigator shall report all suspected device deficiencies to the Sponsor. Device deficiencies will not necessarily result in an AE. However, if an AE is associated with a device deficiency, the AE shall be documented and reported.

11 STATISTICAL ANALYSIS

11.1 Sample Size

A sample size of 300 will provide a precision (defined as the half-width of the two-sided 95% exact binomial confidence interval) of approximately $\pm 6\%$ or smaller for any event based on an incidence of 50%; an observed lower or higher incidence will produce a more precise (i.e. narrower) interval (25).

11.2 Study Outcomes

A number of outcome variables of interest will be collected and assessed across study visits to characterize neurophysiological measures and clinical outcomes with the Evoke System.

11.3 General Statistical Procedures

The following general statistical methods will be employed to assess the study data:

- There are no pre-planned formal statistical hypothesis tests.
- Standard summary statistics will be used to summarize key study variables. Categorical variables will be summarized via incidence and percent. Continuous variables will be summarized via mean, median, standard deviation, and range.
- Findings of significance may be presented and include p-values and/or 95% confidence intervals as appropriate.
- Standard tests for significance will be employed, including one sample t-tests. Additional exploratory analyses may be performed and include correlation analysis, linear and logistic regression analyses, repeated measures analyses, and generalized estimating equation (GEE) analyses as appropriate.
- Unless stated otherwise, statistical significance is defined as achieving a p-value less than 0.05. P-values will be nominal and not adjusted for multiplicity.
- In the event planned parametric methods are found to be inappropriate based upon observed distributions of individual variables, appropriate non-parametric methods will be employed.
- The incidence of all distinct AEs will be presented. AEs will also be summarized by seriousness, severity, and relatedness to the procedure, device, and/or stimulation. AEs will be reported based on the adjudication committee determination.

11.4 Timing of Analyses

As there are no formal pre-planned hypothesis tests, statistical analyses may be completed at any time. Reporting will be completed as required per the regulations and governing IRBs.

12 RISK ANALYSIS

12.1 Potential Risks

Risks associated with the Evoke System are similar to those of other open-loop SCS systems, which are generally minor. All medical procedures involve some risk of injury, including death. Other anticipated risks associated with the Evoke System are listed in this protocol or found in the literature, post-market surveillance data (e.g., FDA Manufacturer and User Facility Device Experience (MAUDE) database), and device labeling for SCS systems. Please refer to the current Evoke IFUs for the most up-to-date risks associated with the Evoke System.

In addition to the general surgical risks, potential risks to subjects associated with implantation and use of the Evoke System include, but are not limited to:

- Undesirable changes in stimulation sensation and/or location
- Uncomfortable changes in stimulation (over and/or under stimulation)
- Persistent post-surgical pain at hardware implantation sites
- CLS migration, which may result in pain or difficulty in charging
- Seroma or hematoma at surgery sites
- Epidural hemorrhage, spinal cord injury and possible paralysis
- Lead migration from the location chosen at initial implantation resulting in stimulation changes
- Breakage of the lead or failure of other system components, which may result in loss of stimulation
- Rejection of, or allergic reaction to, the implanted components
- Infection that may require hospitalization with intravenous antibiotic therapy
- Cerebrospinal fluid (CSF) leakage
- Inadequate pain relief following system implantation
- Erosion of the lead or CLS through the skin
- Weakness, clumsiness, numbness or pain

Subjects may require surgery (including revision, explant, and replacement) as a result of any of the above.

12.2 Minimization of Risks

All known and foreseeable risks associated with the Evoke System have been identified and mitigated with appropriate risk controls to reduce the risk as far as possible.

Risks in this study will be minimized by strict compliance with this protocol, and adherence to the guidelines for subject selection, site training, and close monitoring of the subject status. In addition, the product labeling details instructions for device use, risks, warnings and precautions, which must be followed to minimize risk to subjects. Additionally, only licensed and qualified physicians trained on the Evoke System will implant the device, and device programming will be performed by a trained Sponsor representative with the oversight of the Investigator.

12.3 Potential Benefits

There are several potential benefits of the Evoke System, and specifically with regard to ECAP-controlled closed-loop stimulation, to participating study subjects suffering from chronic, intractable pain of the trunk and/or limbs. These include:

- The Evoke System may provide insight into the neurophysiological mechanisms of chronic pain and SCS.
- The Evoke System may provide significant pain relief.
- The Evoke System may allow patients to reduce their pain medications.
- The Evoke System may improve patients' quality of life, sleep quality, emotional and/or physical functioning.
- The Evoke closed-loop stimulation mode may reduce variation in electrical field strengths reaching the spinal cord due to normal physiological activity and movement.
- The Evoke closed-loop stimulation mode may be more effective in providing pain relief compared to open-loop stimulation.

12.4 Benefit-Risk Conclusions

SCS has been used for over 50 years to aid in the management of chronic, intractable pain of the trunk and limbs. The risks associated with participation in this study are outweighed by the potential benefits and value of the research. The evidence clearly indicates that although there are risks associated with the procedure and the device, the incidence rates are very low, and the majority of complications that can result can be treated. In addition, the procedure itself is completely reversible as the device,

including the leads, can be removed. The Evoke System has the added benefit compared to other SCS systems in that it can measure spinal cord activation resulting from stimulation and use this measure to automatically adjust stimulation current to maintain a target response. By real-time modulation of the output current, the closed-loop system maintains consistent SC activation and thus may maximize the therapeutic effect through the corresponding inhibition of pain processing pathways.

13 STUDY ADMINISTRATION

13.1 Study Materials

13.1.1 Packaging and Labeling

In accordance with 21 CFR Part 812, the study device or its immediate package will bear a label with the following information: the name and place of business of the manufacturer, packer, or distributor (in accordance with 21 CFR Part 801), the quantity of contents, if appropriate, and the following statement: "CAUTION—Investigational device. Limited by Federal (or United States) law to investigational use." Labeling describing all relevant contraindications, hazards, adverse effects, interfering substances or devices, warnings, and precautions are provided in the IFU.

13.1.2 Handling and Storage

The Investigator must ensure that the study devices are controlled and stored according to the IFU. All supplies are to be used only for this study protocol and not for any other purpose. Products are not to be used after the expiration date indicated on the label. The Investigator must not destroy any unused supply unless instructed by the Sponsor.

